12.5.3 Key Secondary Estimands and Multiplicity

The key secondary endpoints will be tested in a hierarchical order following the test of the primary endpoint (see Section 12.0).

Other secondary endpoints will be tested independently without adjustment for multiple tests.

ITT will be used for all key secondary endpoint. Subjects will be included in analyses as randomized. The key secondary endpoints are the time to sustained hospital discharge up to Day 60, supplemental oxygen free days up to Day 29, the proportion of subjects free of respiratory failure at Day 15, and the proportion of subjects discharged and free of supplemental oxygen at Day 15.

12.5.3.1 Missing data

Imputation of data due to intercurrent events (treatment discontinuation due to lack of efficacy, occurrence of important protocol deviation, rescue therapy) will not be performed. Subjects who die will have their missing data set as non-responders in the relevant analysis for all time points of interest following the date of death.

Subjects who discontinue the trial for reasons other than death will have their data multiply imputed as per Section 10.19.1. It is anticipated that missing data will be due to discharged subjects not returning for subsequent scheduled visits, or a worsening of clinical status such that the subject can no longer participate in the trial, or due to missing follow-up visits.

The missing data pattern for the adjusted 8-point ordinal scale will be summarized and a distribution plot will be used to represent the pattern of missing data for the adjusted 8-point ordinal scale showing the proportion of missing data each day per treatment group.

12.5.3.2 Time to Sustained Hospital Discharge

Time to sustained hospital discharge, will be defined as time to discharge after which no re-hospitalizations due to COVID-19 occur. Please refer to Section 10.12 for further details on this calculation.

Treatment groups will be compared using a stratified log-rank test adjusting for treatment, actual baseline disease severity and region. The size of the treatment effect will be estimated as a hazard ratio, obtained using a Cox proportional hazards regression model and the Cox regression model will include a factor for

randomized treatment, baseline disease severity and region. The estimated hazard ratios for each treatment group will be presented together with the corresponding 95% CI (based on Wald test).

Analysis will be illustrated using a Kaplan-Meier plot and the median time to hospital discharge will be estimated with 95% CIs for each treatment group. Subjects who die prior to Day 60 will be censored at Day 60 and trial withdrawals prior to Day 60 due to other causes than death without fulfilling the event will be censored at day of withdrawal. Subjects still in trial but not discharged from hospital at Day 60 will be censored at their Day 60 trial visit.

12.5.3.3 Oxygen Supplemental Free Days up to Day 29

Oxygen supplemental free days up to Day 29 will be defined as the number days for each subject with a score of ≤ 4 and no use of COVID-19 related supplemental oxygen. Refer to Section 10.13 for the derivation of number of oxygen free days.

Subjects who die prior to Day 29 will be given a value of -1 days in the analysis. Subjects who withdraw from the trial prior to Day 29 and have missing data will have their data multiply imputed as per Section 10.19.1. Subjects who chronically used supplemental oxygen prior to their COVID-19 illness will be considered oxygen free when they return to the same level of oxygen support they had been using prior to COVID-19.

Treatment groups will be compared using the Wilcoxon rank-sum test (using p-values) and the treatment difference will be expressed as the Hodges-Lehmann difference in median number of days with 95% CIs. All collected data post treatment will be used. Summary statistics for the number of oxygen free days will also be presented for each treatment group. A cumulative distribution plot of the number of oxygen free days by treatment arm will also be produced.

12.5.3.4 Subjects Free of Respiratory Failure at Day 15

Subjects free of respiratory failure is defined as subject with an ordinal scale score of ≤ 5 at Day 15. A subject is considered a responder for this endpoint if they have a value of ≤ 5 at Day 15.

Treatment groups will be compared using a logistic regression model adjusting for treatment, baseline disease severity and region (as described in Appendix 2). Missing data due to trial withdrawals will be multiply imputed as per Section 10.19.1. Subjects who die prior to Day 15 will be considered non-responders in the analysis. The adjusted proportions as calculated from Ge et al., 2011 and the statistics (treatment difference, SE and CI) following multiple imputation will also be presented. The ITT will be used for the analysis. The number of responders/non-responders will also be presented (these will be the non-imputed values).

12.5.3.5 Subjects discharged and free of supplemental oxygen at Day 15

For this endpoint a subject will be considered a responder in the analysis if the subject has a score of ≤ 2 on the ordinal scale and they are free of supplemental oxygen use at Day 15. Refer to Section 10.10 for details on the classification of subjects as free of supplemental oxygen use at a visit.

Treatment groups will be compared using a logistic regression model adjusting for treatment, baseline disease severity and region (as described in Appendix 2). Missing data due to trial withdrawals will be multiply imputed as per Section 10.19.1. Subjects who die prior to Day 15 will be considered non-responders in the analysis. The adjusted proportions as calculated from Ge et al., 2011 and the statistics (treatment difference, SE and CI) following multiple imputation will also be presented. The ITT will be used for the analysis. The number of responders/non-responders will also be presented (these will be the non-imputed values).

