
 • To explore the effect of C21 versus placebo as add on to SoC on inflammation. 	
 • Change from baseline in CRP at Day 15.

 • To explore the effect of C21 versus placebo as add on to SoC on lung injury. 	
 • Change from baseline in lactate dehydrogenase (LDH) at Day 15.

Primary estimand

All-cause mortality up to Day 60 defined as the time to day of death from any cause assessed for the intention-to-treat population with treatment as randomized, independent of treatment withdrawal or major protocol deviations according to the treatment policy, with subjects with no confirmed death before or at Day 60 being censored at day of withdrawal/Day 60 follow-up. The stratified log-rank test will be used to compare the treatments. The treatment difference will be expressed as a hazard ratio with 95% confidence intervals.

Key Secondary estimands

Time to sustained hospital discharge up to Day 60; The first occurrence of a score ≤ 2 whereafter the score stays ≤ 2 for the remainder of the 60 days trial period, assessed for the intention-to-treat population with treatment as randomized, independent of treatment withdrawal or major protocol deviations according to the treatment policy, with subjects who die prior to Day 60 being censored at Day 60 and subjects withdrawing due to other causes than death and not fulfilling the event being censored at the withdrawal day. The Kaplan-Meier difference in median time to sustained hospital discharge with 95% confidence intervals will be estimated.

Supplemental oxygen free days up to Day 29; For each subject the number of days between Day 1 and Day 29 with a score of ≤ 4 on the 8-point ordinal scale and with no documented use of COVID-19 related supplemental oxygen, assessed for the intention-to-treat population with treatment as randomized, independent of treatment withdrawal or major protocol deviations according to the treatment policy, with subjects who die prior to Day 29 being given the value -1 day and trial withdrawals prior to Day 29 due to other causes than death and not possible to follow-up being imputed using multiple imputation including assessments from day 1 to day 29. The Hodge-Lehmann median estimated of the difference in days between treatments with 95% confidence intervals will be estimated.

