The second key secondary endpoint, oxygen supplemental free days up to Day 29, will be defined as the number days for each subject with a score of ≤ 4 and no use of COVID-19 related supplemental oxygen. Treatment groups will be compared using the Wilcoxon rank-sum test and the treatment difference will be expressed as the Hodge-Lehmann difference in median number of days with 95% confidence intervals. All collected data post-treatment will be used. Subjects who die prior to Day 29 will be given the value of -1 day in the analysis and trial withdrawals prior to Day 29 due to other causes of death will be imputed (for each day) using multiple imputation including status for all of days 1 - 29. The cumulative distribution functions will be plotted to visualize the differences between treatment groups.

The third key secondary endpoint, subjects free of respiratory failure, will be defined as subjects with an ordinal scale score of ≤ 5 at Day 15. Treatment groups will be compared using a logistic regression model adjusting for treatment, baseline disease severity and region. All collected data post-treatment will be used to assess the scores. Subjects who die prior to Day 15 will be considered in respiratory failure and trial withdrawals prior to Day 15 due to other causes than death and not possible to follow-up will be imputed using multiple imputation taking subjects

baseline characteristics and last known status into account. The adjusted proportions as calculated from ([Ge et al., 2011](#)) and the statistics (treatment difference, SE and CI) following multiple imputation will also be presented. The ITT will be used for the analysis. The number of responders/non-responders will also be presented (these will be the non-imputed values).

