8.2 Randomization

Subjects will be randomly assigned in a 1:1 ratio to C21 or placebo treatment. Subject randomization will use a randomly permuted block design and stratified by severity of disease (5 or 6) measured by the 8-point ordinal scale score on trial Day 1 and region.

Registration and randomization will take place using a centralized Interactive Web Response System (IXRS) contracted through Almac. At registration, the IXRS will assign a unique subject identification number that will be used on all of that subject's eCRFs and serious adverse event (SAE) report forms.

This is a double-blinded trial, only a few number of the trial team members are not blinded for conduct of the trial or ensuring subject safety purposes. The unblinded team members will include CRO DMC team members (statistician, programmers and project manager), CRO clinical supply program manager, CRO clinical system designer, CRO clinical system developer and CRO safety personnel. Details are provided in the Data Blinding and Documentation Plan.

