4. Results from the analysis (log-rank, logistic regression as per Appendix 2, statistics from the analysis for number of days oxygen free as per Section 12.5.3.3 and ANOVA) will be combined using Rubin's rule (Rubin, 1987). Estimates will be combined using PROC MIANALYZE in SAS. Rubin's rule assumes the estimates are asymptotically normally distributed.

Analysis of Proportions using Logistic Regression (Appendix 2)

Estimates from the logistic regression are transformed using the method outlined in Appendix 2. The standardized weighted differences, standard errors and the 95% CI based on the delta method (Ge et al, 2011) are approximately normal, no adjustment is required.

Analysis using Log-Rank

Estimates from log-rank are based on a chi-square distributed statistic and prior to combining the estimates via Rubin's rule, the estimates will need to be normalized using a Wilson-Hilferty transformation (Moscovici and Ratitch, 2017).

Analysis using Cox Regression

For results from Cox regression, the estimates obtained from PROC PHREG are log hazard ratios, and after combining via Rubin's rule, the results will be exponentiated to obtain the hazard ratios and associated confidence intervals (Moscovici and Ratitch, 2017).

ANOVA

Estimates from ANOVA are approximately normal and no transformation is required.

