The choice of the subject to change from a survivor to death will be done at random. Using the random seed of 150822, each subject with missing data will be assigned a numeric value. The subject's values will be changed incrementally based on the numeric order generated by this process.

Respiratory Failure Free at Day 15/ Discharged and Free of Supplemental Oxygen Usage at Day 15

For these endpoints, a similar approach as all-cause mortality will be applied. For each imputed dataset as generated per Section 10.19.1 a subject will be assigned as a responder/non-responder depending on the value of the adjusted ordinal scale. For each imputed dataset, a shift will be applied to the number of responders across the imputed datasets. Among the subjects with missing data in the active arm, the number of responders in this group will be reduced incrementally across each dataset, starting at 1 to a maximum value of the number of subjects with missing data at Day 15 or until it is not possible to reduce the number of responders any more in an imputed dataset (i.e all subjects at Day 15 with missing data are set to be non-responder). If a shift is not found by just applying to the active arm, a shift will be applied to the Placebo arm (increasing the number of responders). The choice of which subject to change from responder to non-responder will be assigned following the approach for all-cause mortality.

Number of Supplemental Free Days up to Day 29

For the endpoint oxygen supplemental free days up to Day 29, the imputation as described in Section 10.19.1 will be performed and for each imputed dataset the number of days oxygen free will be tabulated. Then for subjects in the active arm with missing data up to Day 29, the number of days oxygen free will be reduced incrementally starting at 1 up to the number of days the subject had a missing value. For each reduction, the analysis as described in step 3 and step 4 in Section 10.19.1 will be performed. If no tipping point is found by just applying a shift to the number of days in the active arm, the procedure will be repeated with the number of days across subjects with missing data in the placebo arm increased.

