The statistical comparisons for the primary efficacy endpoint and the key secondary endpoints will be carried out in hierarchical order as below:

1. All-cause mortality up to Day 60
2. Time to sustained hospital discharge up to Day 60
3. Supplemental oxygen free days up to Day 29
4. Proportion of subjects free of respiratory failure at Day 15

5. Proportion of subjects discharged from hospital and free of supplemental oxygen at Day 15

This means that statistically significant results for the comparison in the higher rank are required to initiate the testing of the next comparison in the lower rank. All analysis will be performed in the above order, however if a statistical comparison is non-significant then all subsequent statistical analysis will be exploratory in nature and no formal conclusions will be drawn. In other words, if the test for endpoint 3 in the above order is non-significant, then endpoints 4 and 5 will be exploratory in nature.

Since a step-down procedure is used, each comparison will be tested at a significance level of 0.05 and an overall alpha level of 0.05 will be preserved.

All data collected during this trial regarding subject characteristics, efficacy and safety will be listed, unless otherwise specified. Screen failures will be excluded from all listings and tables if not otherwise noted. Listings will not show imputed data but will present data as reported.

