12.5.3.6 Sensitivity Analyses

In order to test the assumptions underpinning the key secondary endpoint analysis the following sensitivity analysis will be performed.

Time to sustained hospital discharge

- 1) Repeated on the PP to assess the impact of important protocol deviations related to efficacy on this endpoint.
- 2) Repeat of the analysis in Section 12.5.3.2 on the ITT where non-COVID-19 related re-admissions are treated as re-admissions due to COVID-19 in the analysis and missing data will be imputed using multiple imputation as described in Section 10.19.1. The median time to sustained discharge will be estimated for each imputed dataset and the average value across each imputed dataset will be presented.

Oxygen Supplemental Free Days up to Day 29

- 1) Repeated on the PP to assess the impact of important protocol deviations related to efficacy on this endpoint.
- 2) Tipping point analysis for the impact of premature trial discontinuation as described in Section 10.19.3.
- 3) Worst Case imputation as per Section 10.19.4.
- 4) An ANOVA model will be fitted for the number of days oxygen free as a response and actual baseline ordinal scale, region and treatment group as factors in the model. This model will be implemented on the imputed datasets as per Section 10.19.1 with the LS means and SEs from the ANOVA models combined using Rubin's Rule (Rubin, 1987).

Subject free of Respiratory Failure at Day 15

- 1) Repeated on the PP to assess the impact of important protocol deviations related to efficacy on this endpoint.
- 2) Tipping point analysis for the impact of premature trial discontinuation as described in Section 10.19.3.
- 3) Worst Case imputation as per Section 10.19.4.

Subjects discharged and free of supplemental oxygen at day 15

- 1) Repeated on the PP to assess the impact of important protocol deviations related to efficacy on this endpoint.
- 2) Tipping point analysis for the impact of premature trial discontinuation as described in Section 10.19.3.
- 3) Worst Case imputation as per Section 10.19.4.

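### Oxygen-free days, third in the fixed sequence, is tested without the randomization strata that the other four hierarchy tests use, which costs power if severity or region is prognostic

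*SAP*

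**What the plan says.** - **Randomization (SAP 8.2).** "Subject randomization will use a randomly permuted block design and stratified by severity of disease (5 or 6"; region is the second stratum.
- **General rule (SAP 12.0, protocol 9.3.1).** The actual strata are to serve as factors in the statistical analysis. SAP 12.0 pools region to Europe versus the rest of the world, so there are 2 x 2 = 4 analysis strata.
- **Ranks 1 and 2 (SAP 12.5.2.2, 12.5.3.2).** Log-rank tests stratified by severity and region.
- **Ranks 4 and 5 (SAP 12.5.3.4, 12.5.3.5).** Logistic regression adjusted for severity and region.
- **Rank 3 (SAP 12.5.3.3, protocol 9.3.3).** The SAP wording is "Treatment groups will be compared using the Wilcoxon rank-sum test (using p-values". The protocol wording is "Treatment groups will be compared using the Wilcoxon rank-sum test", with a Hodges-Lehmann difference. Neither document mentions strata for this test.
- **Adjusted analysis of rank 3 (SAP 12.5.3.6).** "An ANOVA model will be fitted for the number of days oxygen free as a response and actual baseline ordinal scale, region" and treatment. This is a sensitivity analysis outside the hierarchy.
- **Gatekeeping (SAP 12.0).** "statistically significant results for the comparison in the higher rank are required to initiate the testing of the next comparison in the lower rank".

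**The concern.** The severity stratum is the level of oxygen support at baseline: score 5 is supplemental oxygen, score 6 is non-invasive ventilation or high-flow oxygen. It would be surprising if it said nothing about later days free of oxygen. The sponsor's own imputation model for the daily scores (SAP 10.19.1, step 2) includes baseline score and pooled region, and oxygen-free days are counted from those scores.

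Blocking within strata makes the arms nearly balanced on severity and region, so the treatment contrast varies less than it would under simple randomization. The plain rank-sum variance ignores this and still includes the between-stratum part. When the strata are prognostic, the test statistic is too small on average and the true size falls below 5%.

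A miss at rank 3 also makes ranks 4 and 5 exploratory. The plan states no power for this endpoint, and amendment 4 cut the maximum sample size from 600 to 300.

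**Working it through.** **The plan's own figure.** Power is stated only for mortality: 80% for 10% versus 2.5% dead at Day 60, 150 per arm, 5% withdrawal. This reproduces. HR = ln(0.975)/ln(0.90) = 0.240, and a log-rank simulation (exponential survival, 4,000 runs) gives 80.0%. For 15 versus 6 deaths, z = (15 − 6)/√21 = 1.964, p = 0.0495. There is no corresponding figure for oxygen-free days.

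**Analytic approximation for rank 3 (ties ignored, severity only).** Let p be the share of subjects with score 6 and θ the chance that a score-6 subject has the worse result of a score-6/score-5 pair. Both are assumptions.

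- Share of rank variance explained by severity: R² = 12·p(1 − p)(θ − 0.5)²
- True size of the plain test: 2[1 − Φ(1.96/√(1 − R²))]
- Power of the plain test when the stratified test has 80%: 1 − Φ(1.96/√(1 − R²) − 2.80)

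Example, p = 0.25 and θ = 0.70: R² = 12 × 0.1875 × 0.04 = 0.090; 1.96/√0.910 = 2.055; size 4.0%; power 77.25%, a loss of about 2.8 points.

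| p | θ | R² | Size | Power | Loss (points) |
|---|---|---|---|---|---|
| 0.10 | 0.60 | 0.011 | 4.9% | 79.7% | 0.3 |
| 0.10 | 0.70 | 0.043 | 4.5% | 78.8% | 1.2 |
| 0.10 | 0.80 | 0.097 | 3.9% | 77.0% | 3.0 |
| 0.25 | 0.60 | 0.023 | 4.7% | 79.4% | 0.6 |
| 0.25 | 0.70 | 0.090 | 4.0% | 77.3% | 2.8 |
| 0.25 | 0.80 | 0.203 | 2.8% | 72.8% | 7.2 |
| 0.50 | 0.60 | 0.030 | 4.7% | 79.2% | 0.8 |
| 0.50 | 0.70 | 0.120 | 3.7% | 76.2% | 3.8 |
| 0.50 | 0.80 | 0.270 | 2.2% | 69.4% | 10.6 |

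Losses are rounded from unrounded values.

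**Simulation with ties and deaths.** 300 subjects, 4 strata, blocks of 4, 0–28 days, death = −1, no missing data. Assumed deaths before Day 29 were 5% for score 5 and 15% for score 6 (5% throughout when the strata are not prognostic). There were 4,000 trials per power scenario. Power, plain versus van Elteren:

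- not prognostic: 84.0% vs 83.6%
- R² about 0.05: 82.9% vs 84.0%
- R² about 0.11: 80.2% vs 83.3%
- R² about 0.22: 73.0% vs 81.6%

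Null rejection (12,000 trials) was 4.9% vs 4.9% when not prognostic, 4.2% vs 4.6% at R² 0.05 and 3.9% vs 5.2% at R² 0.12.

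**Second simulation under other assumptions.** 30% score 6, 50% Europe, treatment shift 0.325 SD on a latent scale, 4,000 runs per cell, Monte Carlo error about 0.7 points on power. Severity/region effects are in latent SD:

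| Effects | Plain | van Elteren | Size of plain test |
|---|---|---|---|
| 0 / 0 | 79.0% | 78.2% | 4.3% |
| 0.5 / 0 | 75.9% | 77.1% | 4.9% |
| 0.5 / 0.25 | 76.6% | 78.3% | 4.3% |
| 1.0 / 0 | 69.9% | 76.3% | 3.4% |
| 1.0 / 0.5 | 69.5% | 77.5% | 2.7% |
| 1.5 / 0.5 | 61.3% | 77.5% | 1.8% |

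The van Elteren size stayed between 4.4% and 5.4%. All three calculations agree in direction and, for comparable stratum effects, in rough size.

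**The case against.** **The strata may be weakly prognostic here.** Exclusion criterion 9 removes subjects with SpO2/FiO2 of 232 or less, but only if they are on non-invasive ventilation or high-flow oxygen. A score-6 subject assessed that way has FiO2 below about 0.39–0.42 (0.90/2.32 to 0.98/2.32, at SpO2 90–98%). Score-5 subjects have no such limit, and SAP Appendix 3 lists low-flow masks delivering 60–100%. The two strata can overlap heavily. With θ of 0.55–0.65 and 25% score 6, the formula gives a loss of only 0.2–1.5 points. This stands as a reason to expect the lower part of the range; it does not show that severity is uninformative.

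**The top end is a corner case.** The 10.6 points need both a 50% score-6 share and θ = 0.80, and the documents support neither. That is fair.

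**80% power is an assumed anchor.** Rank 3 is reached only after mortality and sustained discharge succeed, and deaths enter it as −1, so the tests are positively related. Power in trials that reach rank 3 could well exceed 80%. At 25% and θ = 0.70 the loss is 2.8 points at 80% power, 1.8 at 90% and 1.1 at 95%. This too bears on size only.

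**Nothing is invalid.** The test is pre-specified, protocol and SAP agree, and an adjusted ANOVA is planned. All true, but the ANOVA cannot rescue a failed hierarchy test. The plan gives no reason for departing from its own rule on strata at this one rank.

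**Conclusion.** The concern holds as a matter of efficiency and consistency. Rank 3 is the only hierarchy test that ignores the randomization strata. Under the assumed 10–50% score 6 and θ of 0.60–0.80, the loss is 0.3 to 10.6 points against a stratified test with 80% power, and the true size falls from 4.9% to as low as 2.2%. Criterion 9 makes the lower part of that range more likely than the top, and the loss is nil if neither stratum is prognostic. Region could add to it.

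These losses are conditional on ranks 1 and 2 being significant. Type I error is protected throughout. The change is still worth making because the balance is one-sided: stratifying costs 0.4 and 0.8 points in the two simulations when the strata are irrelevant (84.0 vs 83.6; 79.0 vs 78.2) and recovers several points when they matter.

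**What to change.** Before unblinding:

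1. **SAP 12.5.3.3 and Appendix 1.** Make the hierarchy test a van Elteren (stratified Wilcoxon) test by actual baseline severity and pooled region (4 strata). Report a matching Hodges-Lehmann estimate, for example from within-stratum pairwise differences with an interval obtained by inverting the same test. Name one estimator and one interval method.
2. **SAP 10.19.1, step 4.** The step lists "statistics from the analysis for number of days oxygen free as per Section 12.5.3.3" among the results to be pooled by Rubin's rule. It gives pooling detail for logistic regression, log-rank, Cox and ANOVA, but none for the rank-sum result. State the rule; one option is to pool the standardized van Elteren statistic with within-imputation variance 1. This gap exists with or without stratification and is conveniently closed in the same edit.
3. **SAP 10.19.3.** The tipping-point text reads "For each reduction, the analysis as described in step 3 and step 4 in Section 10.19.1 will be performed". Confirm that these runs use the stratified test.
4. **SAP 6.1.** Record the departure from protocol 9.3.3 and from the protocol section 3 estimand, which specifies "The Hodge-Lehmann median estimated of the difference in days between treatments", or amend the protocol.

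Extending the change to the Wilcoxon endpoints in SAP 12.5.4 is optional, since they lie outside the hierarchy.

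The cost is a few SAP edits and programming, with no new data. The real burden is the formal one of changing a pre-specified test and estimate in a signed version 2.0 SAP, so the entry should state that the change was made blind.
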